## 7.2 Inclusion and exclusion criteria for the elderly

## **Inclusion criteria:**

- 1. Male or female subjects ≥65 years old and ≤85 years old at Screening Visit.
- 2. Individuals who are in a health condition that can receive the investigational vaccine, at the time of entry into the trial as determined by medical history, physical examination (including vital signs, ECG) and eligibility screening tests (hematology, biochemistry and urinalysis) and clinical judgment of the investigator at Screening Visit.
- 3. The subject can provide with informed consent and signs and dates a written informed consent form (ICF) prior to the initiation of any trial procedures.
- 4. They must be able to understand and follow trial-related instructions.
- 5. They must be willing and able to comply with planned visits, treatment schedule, laboratory tests and other requirements of the trial.

- 6. Negative in antibodies screening of SARS-CoV-2 (blood sample from fingertip).
- 7. No imaging features of COVID-19 in chest CT scan.
- 8. Axillary temperature≤37.0°C.
- 9. Negative SARS-CoV-2 test in throat swabs by RT-PCR. Women of childbearing potential (WOCBP) must have a negative serum β-hCG at Screening Visit. Women that are postmenopausal (Menopause≥12 consecutive months) or permanently sterilized will be considered as not having reproductive potential.
- 10. Women of childbearing potential (WOCBP) must have a negative serum β-hCG at Screening Visit. Women that are postmenopausal (Menopause ≥12 consecutive months) or permanently sterilized will be considered as not having reproductive potential.
- 11. WOCBP must have used effective contraception 14 days prior to screening and agree to use effective contraception continuously during the trial period, from 14 days prior to Screening Visit to 60 days after the last immunization.
- 12. WOCBP must agree not to donate eggs (ova, oocytes) for the purposes of assisted reproduction during trial, starting from Screening Visit and continuously until 60 days after be given the last immunization.
- 13. Men who are sexually active with a WOCBP and have not had a vasectomy must agree to practice a effective form of contraception with their female partner of childbearing potential during the trial, starting from Screening Visit and continuously until 60 days after be given the last immunization.
- 14. Men must be willing to refrain from sperm donation, starting from Screening Visit and continuously until 60 days after receiving the last immunization.

#### **Exclusion criteria:**

- 1. Physical examination and qualifying screening during screening visits, finding baseline laboratory abnormalities  $\geq$ grade 3 (for hematology abnormalities with Grade  $\geq$ 2, according to grading criteria in Appendix B).
- 2. Have had any acute illness, as determined by the investigator, with or without fever, within 72 h prior to the prime vaccination. An acute illness which is nearly resolved with only minor residual symptoms remaining is allowable if, in the opinion of the investigator, the residual symptoms will not compromise their well-being if they participate as trial subjects in the trial, or that could not prevent, limit, or confound the protocol-specified assessments.
- 3. Have a known allergy, hypersensitivity, or intolerance to the planned vaccine for trial including any excipients.
- 4. Used to have a history of hypersensitivity or serious reactions to vaccinations.
- 5. Received any vaccination within 4 weeks prior to Visit 1.
- 6. The subject doesn't agree to avoid vaccination during the trial, starting from Screening Visit and continuously until 28 days after receiving the last immunization, except emergency vaccination (e.g. rabies vaccine, tetanus vaccine).

- 7. Had administration of any immunoglobulins and/or any blood products within the 3 months prior to Screening Visit.
- 8. Had any serious or life-threatening medical condition (e.g., autoimmune disease, cardiovascular disease) within the past 5 years, which in the opinion of the investigator, could compromise their well-being if they participate as trial subjects in the trial, or that could prevent, limit, or confound the protocol-specified assessments.
- 9. Have any surgery planned during the trial, starting from Screening Visit and continuously until at least 90 days after the last immunization.
- 10. Had any chronic use (more than 14 continuous days) of any systemic medications, including immunosuppressant or other immune-modifying drugs, within 6 months prior to Screening Visit unless in the opinion of the investigator, the medication would not prevent, limit, or confound the protocol-specified assessments or could compromise safety of subjects.
- 11. Had administration of another investigational product including vaccines within 60 days or 5 half-lives (whichever is longer), prior to Screening Visit.
- 12. With known history of AIDS or HIV test positive.
- 13. Have infection history of HBV or HCV.
- 14. History of SARS, SARS-CoV-2 or MERS infection. Suspected SARS patients should be screened for SARS antibodies.
- 15. Previously participated in a clinical trial involving lipid nanoparticles.
- 16. Are subject to exclusion periods of other clinical trials or simultaneous participation in another clinical trial.
- 17. Have any affiliation with the study site (e.g., are close relative of the investigator or dependent person, such as an employee or student of the study site).
- 18. Have a history of drug abuse or known medical, psychological or social conditions within the past 5 years. In the opinion of the investigator, could comprise their well-being if they participate as trial subjects in the trial, or that could prevent, limit, or confound the protocol-specified assessments.
- 19. Have a history of narcolepsy.
- 20. Have history of alcohol abuse or drug addiction within 1 year prior to Screening Visit.
- 21. Have a history of or suspected immunosuppressive condition, acquired or congenital, as determined by medical history and/or physical examination at Screening Visit.
- 22. Have any abnormality or permanent body art (e.g., tattoo), in the opinion of the investigator, would obstruct the ability to observe local reactions at the vaccination site.
- 23. Have had any blood loss >400 mL, e.g., due to donation of blood or blood products or injury, within the 28 days prior to Screening Visit or plan to donate blood or plasma during the trial, starting from Screening Visit and continuously until at least 28 days after be given the last immunization.
- 24. Travel or live in any country or region with a high SARS-CoV-2 infection risk (as defined at

Screening Visit) within the 14 days prior to Screening Visit.

- 25. They plan to visit any country or region with a high SARS-CoV-2 infection risk (as defined at Screening Visit), from Screening Visit until 14 days after be given the last immunization.
- 26. Symptoms of COVID-19, e.g., respiratory symptoms, fever, cough, shortness of breath and breathing difficulties.
- 27. Have had contact with confirmed COVID-19 patients or persons tested positive for SARS-CoV-2 nucleic acids or antibodies within the 30 days prior to Screening Visit.
- 28. Are vulnerable persons, e.g., soldiers, subjects in detention, CRO or Fosun staffs or their family members.

#### 8.0 VACCINATION AND MANAGEMENT OF VACCINE

This section contains the information of the investigational drug needed for the protocol, including vaccination and management of vaccine.

#### 8.1 Vaccination

# 8.1.1 Investigational vaccine/ placebo

# Investigational vaccine:

The drug product is a preservative-free, sterile dispersion of RNA formulated in lipid nanoparticles (LNP) in aqueous cryoprotectant buffer for intramuscular administration. The RNA drug substance is the only active ingredient in the drug product. For dispensing and operation protocol, see Pharmacy Manual.

Frequency of Two injections (21 days apart).

vaccination:

Route of vaccination: Intramuscular (IM); upper arm, musculus deltoideus; the P/B regimens.

The same arm may be used for both immunizations. The non-dominant

arm is preferred.

#### Placebo:

NaCl 0.9% solution is being used as placebo. It is a sterile, clear, colorless liquid solution of sodium chloride without preservative designed for parenteral use only. The placebo is commercially available packaged and stored according to the labelling. The placebo is vaccinated by IM at 21-day intervals.

## 8.1.2 Preparation/handling/storage/accountability

The preparation of solution for injection will be carried out by the pharmaceutical professionals or other trained personnel at the trial site according to the sterile operation procedures.

For instructions on preparation, handling and storage of investigational drugs (IMP BNT162b1 vaccine), see the Pharmacy Manual.

The investigator or designee must confirm appropriate temperature conditions have been maintained during transit for all IMP received and any discrepancies are reported and resolved before use of IMP.

Only subjects enrolled in the trial may receive IMP and only authorized site unblinded personnel may administer IMP. All IMP (and any components thereof) must be stored in a safe, environmentally controlled, and monitored (manual or automated) area in accordance with the labeled storage conditions with access limited to the investigator and authorized study site personnel.

The investigator, study site, or the head of the site (where applicable) is responsible for storage, checking, and record maintenance (i.e., receipt, check and final disposition records) of IMP (and any components thereof).

Further guidance and information for the final disposition of unused IMP (and any components thereof) is provided in the Pharmacy Manual.

# 8.1.3 Dose and regimen

Each randomized subject will receive BNT162b1 (low-dose and high-dose) or placebo intramuscularly (IM) for two times – one injection at Visit 1 (on Day 1) and one injection at Visit 5 (on Day 22) IM into the one third of the deltoid muscle, preferably in the non-dominant arm. The additional doses may be explored, and the details will be provided in the pharmacy manual

#### Planned cohorts:

- Cohort 1: BNT162b1 low-dose (10 μg);
- Cohort 2: BNT162b1 high-dose (30 μg);
- Cohort 3: placebo.

## 8.2 Allocation, preparation and injection procedures of investigational vaccine/placebo

According to the instructions of the Pharmacy Manual, the designated qualified non-blind personnel shall regulate, prepare and inject investigational vaccine/placebo. All investigational vaccine/placebo preparation will be documented.

The investigator or designee will be responsible for overseeing the administration of investigational vaccine/placebo to subjects enrolled in the trial according to the procedures stipulated in this trial protocol.

Standard immunization practices are to be observed and care should be taken to administer the injection intramuscularly. Before administering the vaccine, the vaccination site is to be disinfected with a skin disinfectant (eg, 70% alcohol). And allow the skin to dry.

As with all injectable vaccines, trained medical personnel and appropriate medical treatment should be readily available in case of anaphylactic reactions following vaccination.

# 8.3 Randomization code creation and storage

The method of block randomization will be used, and the random table of subjects will be generated by an independent randomized professional through SAS9.4 or above, and will be imported to the interactive response technology (IRT) system, which could only be accessed by authorized personnel. Subjects, researchers and sponsor study management will remain blinded throughout the trial. The authorized unblinded staff of the research center can obtain the subject allocation information through the IRT system and allocate the experimental vaccine or placebo of the corresponding group according to the allocation information.

All selected subjects will be assigned a screening number. For the selected subjects, the IRT system was used for randomization and a random number was obtained (the random number was used as the unique subject ID number). The random parameters and Settings are described in detail in the randomization specification.

## 8.4 Maintain of blinding

The trial is a blinding study for subjects and observers. The subjects, data collectors (eg, investigator), and data evaluators (eg, trial statisticians) are blinded. The investigational product assignment will be maintained by the unblinded site staff designee. It is no need of blinding for investigational products.

All care must be taken to ensure that the unblinded reports and documents are shared only with unblinded personnel and properly stored in a secured area, accessible only by authorized personnel. All non-blinded personnel, including dispensers and vaccination nurses, are required to sign confidentiality agreements.

## 8.5 Unblinding procedures

The investigational vaccine/placebo blind shall not be broken by the investigator unless information concerning the investigational vaccine/placebo is necessary for the medical treatment of the subject. In the event of a medical emergency, if possible, the medical monitor should be contacted before the investigational vaccine/placebo blind is broken to discuss the need for urgent unblinding.

The Fosun's Pharmacovigilance Department must be notified as soon as possible if the investigational vaccine/placebo blinding is broken by the investigator; and if the unblinding was for medical reasons (SAE), the completed SAE form must be sent within 24 hours (ie, follow the standard process for reporting of SAEs). The date, time, and reason the blind is broken must be recorded in the source document and the same information (except the time) must be recorded on the eCRF.

Unblinding will be occurred at the initial analysis of safety and immunogenicity 28 days after boost vaccination, but the subjects will be kept blinded.

## 9.0 TRIAL PLAN

# 9.1 Trial procedures

The following sections describe the trial procedures and data to be collected. For each procedure, subjects are to be assessed by the same investigator or site personnel whenever possible. The Schedule of Trial Procedures is located in **Table** 2.

#### 9.1.1 Informed consent

Informed consent must be obtained at Screening Visit, prior to the subject entering into the trial and before any protocol-directed procedures are performed.

A screening number will be assigned at Screening Visit to each subject after informed consent is obtained. If all eligibility criteria are fulfilled, a randomization number (the unique subject ID number) will be assigned, and this subject ID number will be used throughout the trial. Subject screening numbers assigned to subjects who fail screening should not be reused (Section 9.1.10).

# 9.1.2 Demographics, medical history, travel history, prior/concomitant medications/vaccinations, and blood donation

Demographic information, to be obtained at Screening Visit, will include age (date of birth), sex, race, and ethnicity as provided by the subject. See Section 6.1 for more details about the enrollment.

Medical history will also be collected at Screening Visit and at Visit 1 (Day 1) pre-vaccination and will include any medical history that may be relevant to subject eligibility for trial participation such as prior vaccinations, concomitant medications, and previous and ongoing illnesses or injuries. Relevant medical history can also include any medical history that contributes to the understanding of an AE that occurs during trial participation, if it represents an exacerbation of an underlying disease/preexisting problem.

Medical occurrences before administration of the first dose of investigational vaccine/placebo are considered medical history.

Travel history to SARS-CoV-2 endemic countries and SARS-CoV-2 endemic regions of China within 2 weeks prior to screening will be collected at Screening Visit. Travel history to SARS-CoV-2 endemic countries and SARS-CoV-2 endemic regions of China will be collected at each visit.

Ask the subject's medical history, record the following medication of the subject: 4 weeks within the vaccincation, long-term use of systemic medication affecting the immune function within 6 months, immunoglobulin and/or blood products within 3 months, take another kind of study drug (including vaccine) within 60 days or five half-life (will be subject to a long time). And all medications, vaccines and blood products taken or received by the subjects within 1 monthprior to the start of the trial are to be recorded on the source document (patient record) and entered on the Prior and Concomitant Medications eCRF. The use of antipyretics and/or analgesic medications within 24 hours prior to vaccination must be identified and the reason for their use (prophylaxis versus treatment) must be described in the source documents and the eCRF.

# Contradicted medication/treatment (See Section 7.0)

- Had any chronic use (more than 14 continuous days) of systemic medications affecting immune function, including immunosuppressant or other immune-modifying drugs, within 6 months prior to Screening Visit unless in the opinion of the investigator, the medication would not prevent, limit, or confound the protocol-specified assessments or could compromise safety of subjects.
- Received any vaccine within 4 weeks prior to Visit 1.
- Had administration of any immunoglobulins and/or any blood products within the 3 months prior to Screening Visit.
- Had administration of another investigational product including vaccines within 60 days or 5 half-lives (whichever is longer), prior to Screening Visit.

Subjects should not donate blood during the main study period (starting after screening visit and continuously until at least 28 days after receiving the last immunization).

Medical history (including corresponding medication) to be obtained will include any significant conditions or diseases that have disappeared or resolved at or prior to signing of informed consent.

# 9.1.3 SARS-CoV-2 testing

All subjects will be tested for SARS-CoV-2 at Screening Visit, including oropharyngeal swabs through RT-PCR and fingertip blood will be collected for SARS-CoV-2 antibodies screening.

The anti-SARS-CoV-2 antibody testing will be performed with a commercially available antibody test. It will be used to test subjects who may have experienced enhanced respiratory disease or progression of flu-like symptomatology, such as non-resolution of the symptoms after 7 d, symptom kinetics that are inconsistent with a relationship to RNA immunization, as might be expected with a COVID-19 disease (See Section 10.5).

## 9.1.4 Physical examination

The physical examination must be carried out by qualified health professionals in accordance with the relevant regulations and the licensing requirements designated with the "Site Authorization Form". Complete physical examination, including height, will be performed at Screening Visit according to the investigator's standard practice. Measurement of height is only required at Screening Visit. BMI will be calculated using standard BMI calculator.

Additional symptom-directed physical examinations may be performed at following visits if deemed necessary or indicated by review of the subject's medical history, and should assess clinically significant changes from the baseline examination.

The following should be documented in the subject's source document and transcribed into the eCRF:

- The findings of complete physical examinations;
- the findings of symptom-directed physical examinations;

• if symptom-directed physical examinations were not required.

## 9.1.5 Vital signs, 12-lead ECG and chest CT scan

Vital signs include systolic/diastolic blood pressure, pulse rate, respiratory rate, and body temperature. Measurement of body weight is only required at Screening Visit. Follow standard of care for trial population and operational feasibility.

Vital signs must be within normal limits (ie, below Grade 1 as specified in the NMPA Toxicity Grading Scale for Healthy Adult Volunteers, see Appendix B).

12-lead ECG and Chest CT scan will be performed at Screening Visit. Chest CT images must have no imaging features of COVID-19.

In the event of abnormal ECG, heart rate or blood pressure due to physiological variation or activity, the subject may rest for 10 minutes in a quiet room, and then ECG, blood pressure and/or heart rate may be re-measured. Repeated ECG or vital signs may be used to determine eligibility.

# 9.1.6 Blood sample and urine sample collection

Blood samples will be collected at each site visit: ie, at Screening Visit for eligibility screening tests (clinical laboratory testing, see Section 9.1.6.3), at Visits 2, 3 and 6 for routine safety laboratory testing (see Section 9.1.6.4 for Visits 2, 6 coagulation function test, Visits 2, 6, 11 thyroid function test). Blood samples for immunogenicity (anti-S1/anti-RBD IgG and SARS-CoV-2 neutralizing antibody) will be collected at Visits 1, 5, 6, 8, 10, 11 and 12 for adults and at Visits 1, 5, 6, 8, 11 and 12 for the elderly (see Section 9.1.6.5).

Should a blood sampling be performed during a vaccination visit, this sampling must occur before the injection of the investigational vaccine or placebo. Serum sample will be collected for women of childbearing potential at Screening Visit and Visit 5 before each investigational vaccine/placebo injection for pregnancy testing (see Section 9.1.9). Figertip blood samples will be collected at Screening Visit for SARS-CoV-2 serostatus determination (see Section 9.1.6.1) and HIV serostatus determination (see Section 9.1.6.2).

Urine samples will be collected for all subjects at Screening Visit for eligibility screening (see Section 9.1.6.3), and at Visits 2, 3 and 6 for routine safety laboratory testing (see Section 9.1.6.4).

All samples will be collected in accordance with acceptable laboratory procedures. Samples of immunogenicity and CMI testing will be processed and stored at the study site as described in the provided Laboratory Manual.

# 9.1.6.1 SARS-CoV-2 antibody test

All subjects who sign the ICF will be tested for SARS-CoV-2 antibody test (fingertip blood) at Screening Visit.

## 9.1.6.2 HIV test

All subjects who sign the ICF will be tested for HIV antibody at Screening Visit. For screening, the subject's fingertip blood will be collected for anti-HIV antibodies.

# 9.1.6.3 Screening laboratory testing

Screening laboratory testing that will be performed on blood and urine samples at Screening Visit are outlined in **Table** 4.

Subjects of adults must have laborat ory values within normal limits or not be above Grade 1 as defined in Appendix B within 7 days before enrollment, and Grade 2 for the elderly. If the results of laboratory screening testing are out of acceptable range, repeat of screening tests is permitted once, provided there is an alternative explanation for the out of normal range value.

Should the respective repeated test results be available within the screening period, no new subject screening numbers will be required; the repeated screening tests will be recorded in the appropriate CRF (unscheduled lab form). Should the respective repeated test results not be available within the screening period, the subject would need to be screen failed and all screening procedures and tests would need to be repeated with a new subject screening number.

Blood samples for screening laboratory testing will be approximately 15 mL.

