#### **Exclusion criteria:**

- 1. Baseline laboratory abnormalities with Grade ≥3 (for hematology abnormalities with Grade ≥2, according to the grading criteria in appendix B) during screening visits, by physical examination and eligibility screening.
- 2. Have had any acute illness, as determined by the investigator, with or without fever, within 72 h prior to the prime vaccination. An acute illness which is nearly resolved with only minor residual symptoms remaining is allowable if, in the opinion of the investigator, the residual symptoms will not compromise their well-being if they participate as trial subjects in the trial, or that will not prevent, limit, or confound the protocol-specified assessments.
- 3. Have a known allergy, hypersensitivity, or intolerance to the planned vaccine for trial including any excipients.

- 4. Used to have a history of hypersensitivity or serious reactions to vaccination.
- 5. Received any vaccination within 4 weeks prior to Visit 1.
- 6. Don't agree to not be vaccinated during the trial, starting from Screening Visit and continuously until 28 days after receiving the last immunization, except emergency vaccination (e.g. rabies vaccine, tetanus vaccine).
- 7. Had administration of any immunoglobulins and/or any blood products within the 3 months prior to Screening Visit.
- 8. Had any serious or life-threatening medical condition (e.g., autoimmune disease, cardiovascular disease) within the past 5 years, which in the opinion of the investigator, could compromise their well-being if they participate as trial subjects in the trial, or that could prevent, limit, or confound the protocol-specified assessments.
- 9. Have any surgery planned during the trial, starting from Screening Visit and continuously until at least 90 days after the last immunization.
- 10. Had any chronic use (more than 14 continuous days) of any systemic medications that affects immune function, including immunosuppressant or other immune-modifying drugs, within 6 months prior to Screening Visit unless in the opinion of the investigator, the medication would not prevent, limit, or confound the protocol-specified assessments or could compromise safety of subjects.
- 11. Had administration of another investigational product including vaccines within 60 days or 5 half-lives (whichever is longer), prior to Screening Visit.
- 12. With known history of AIDS or HIV test positive.
- 13. History of HBV or HCV infection.

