## 7.0 Inclusion and exclusion criteria

All entry criteria, including test results, need to be confirmed prior to randomization.

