## 9.1.10 Documentation of trial entrance/randomization

Only subjects who have signed an ICF at Screening Visit, meet all of the inclusion criteria and none of the exclusion criteria, are eligible for allocation/randomization into the vaccination phase.

One single subject screening number will be assigned to each subject at Screening Visit. In the study, subjects will be randomized at 1:1:1 with each cohort of 24 subjects to inject BNT162b1 or placebo.

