# 9.3.1 Screening procedures (Screening Visit)

See Section 6.1 for more details about the enrollment.

The following screening procedures will be performed at Screening Visit:

- 1. Confirm informed consent, and complete and collect ICF (see Section 9.1.1). Before performing any other trial procedure, the signed ICF needs to be obtained. Only applicable for newly screened subjects.
- 2. Assign subject ID number (see Section 6.1 for more details about the enrollment).
- 3. Assess eligibility criteria (see Sections 7.1 and 7.2).
- 4. Collect demographics (see Section 9.1.2).
- 5. Collect medical history (including alcohol taken), travel history (to SARS-CoV-2 endemic countries and SARS-CoV-2 endemic regions of China), and prior/concomitant medications/vaccinations (see Section 9.1.2).
- 6. Perform "complete" physical examination (see Section 9.1.4).
- 7. Check vital signs (see Section 9.1.5).
- 8. Perform 12-lead ECG and chest CT test (see Section 9.1.5).
- 9. Collect blood sample for eligibility screening tests (hematology, biochemistry, see Section 9.1.6).
- 10. Collect fingertip blood for SARS-CoV-2 and HIV antibody.
- 11. Collect oropharyngeal swabs for SARS-CoV-2 testing.
- 12. Collect urine sample for eligibility screening urinalysis.
- 13. For WOCBP, serum pregnancy testing will be performed at Screening Visit (see Section 9.1.6 for pregnancy test), and contraception guidance will be provided (see Section 9.1.8 and 9.1.9).

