# 9.3.2 Pre-vaccination procedures

The following procedures will be performed at Visit 1 (Day 1) and Visit 5 (Day 22):

- 1. Collect medical history, travel history (to SARS-CoV-2 endemic countries and SARS-CoV-2 endemic regions of China), and concomitant medications/vaccinations (see Section 9.1.2).
- 2. Perform symptom-directed physical examination (if deemed necessary, see Section 9.1.4).
- 3. Assess eligibility criteria (see Sections 7.1 and 7.2) at Visit 1 (Day 1).
- 4. Check vital signs (see Section 9.1.5).
- 5. Randomize subject (only at Visit 1 on Day 1), a random number was obtained (the random number was used as the unique subject ID number) (see Section 9.1.10).
- 6. Collect blood sample for clinical laboratory and immunogenicity assessment (see Section 9.1.6).
- 7. For WOCBP, serum pregnancy testing will be performed before boost vaccination (see Section 9.1.9).

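### Protocol 9.1.6.3 lets an elderly Grade 2 haematology value pass at screening, but elderly exclusion criterion 1 disqualifies it

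*Protocol*

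**What the plan says.** Protocol 9.1.6.3 requires adult screening values to be normal or no worse than Grade 1, "as defined in Appendix B within 7 days before enrollment, and Grade 2 for the elderly". The panel it refers to (the clinical laboratory table that follows) includes haematology. The section then adds: "If the results of laboratory screening testing are out of acceptable range, repeat of screening tests is permitted once", subject to there being another explanation for the value. It does not define the acceptable range separately.

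Elderly exclusion criterion 1 in the trial summary (Protocol 2.0) excludes laboratory abnormalities of Grade 3 or worse, with a tighter limit "for hematology abnormalities with Grade ≥2, according to the grading criteria in appendix B". Section 7.2 repeats this rule.

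Three other places decide which rule controls entry:

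- Section 7.0: "All entry criteria, including test results, need to be confirmed prior to randomization".
- Section 9.1.10: only consenting subjects who "meet all of the inclusion criteria and none of the exclusion criteria, are eligible for allocation/randomization into the vaccination phase".
- Sections 9.3.1 and 9.3.2: eligibility is checked against 7.1 and 7.2 at Screening and again on Day 1.

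**The concern.** Two current sections of Version 3.0 give different thresholds for the same screening decision on the same grading scale. Section 9.1.6.3 is where site staff would look when laboratory results come back, and for elderly haematology it states the looser limit.

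Two things are at stake. A site working from 9.1.6.3 could enrol an elderly subject whom criterion 1 excludes. And if the acceptable range means the limits in the sentence just before it, a Grade 2 haematology value is in range and prompts no repeat, so a subject with an explainable value could be lost without the retest that the section otherwise allows.

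The amendment log in Appendix E gives preliminary safety data from the Germany and US trials as the reason for the tighter haematology limit. It is therefore a deliberate safety restriction that 9.1.6.3 does not carry.

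**Working it through.** The plan states no figure on this point, so the check compares the two rules grade by grade.

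**Step 1. The rules for an elderly subject, both on Appendix B.**
- Section 9.1.6.3: acceptable if grade ≤ 2, for every laboratory parameter.
- Criterion 1: acceptable if grade < 3; for haematology, acceptable only if grade < 2.

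**Step 2. Comparison.**

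| Grade | Haematology: 9.1.6.3 | Haematology: criterion 1 | Other: 9.1.6.3 | Other: criterion 1 |
|---|---|---|---|---|
| 0 | pass | pass | pass | pass |
| 1 | pass | pass | pass | pass |
| 2 | **pass** | **exclude** | pass | pass |
| 3 | fail | exclude | fail | exclude |
| 4 | fail | exclude | fail | exclude |

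Of the ten combinations, one conflicts: haematology at Grade 2.

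**Step 3. Values in the conflicting cell** (Appendix B Table 5, seven graded parameters, counting white cells high and low separately).
- White cells high: 13 to <15; low: 1.500 to 1.999 (10⁹/L)
- Lymphocytes: 0.5 to 0.749 (10⁹/L)
- Neutrophils: 0.600 to 0.799 (10⁹/L)
- Eosinophils: 1.51 to 5.0 (10⁹/L)
- Platelets: 100 to 124 (10⁹/L)
- Haemoglobin: 9.0 to <10.0 g/dL in men, 8.5 to <9.5 g/dL in women

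**Step 4. Consequence for analysis sets.** Protocol 13.1.1 lists meeting an exclusion criterion as a major violation that removes a subject from the per-protocol set. SAP section 6 limits this to major criteria, so removal is possible but not certain. With about 24 subjects per arm in each age group, one removal is 1/24 = 4.2% of an arm.

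**Step 5. Check of the fix.** With haematology acceptable at grade ≤ 1 and other values at grade ≤ 2, 9.1.6.3 agrees with criterion 1 in all ten cells.

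**The case against.** The strongest defence is that 9.1.6.3 states a necessary condition, not a sufficient one. Criterion 1 adds a stricter condition, and a subject can satisfy both. Sections 7.0, 9.1.10, 9.3.1 and 9.3.2 all lead to the eligibility criteria before randomization. This stands. A reader might infer that the protocol permits dosing an elderly subject with Grade 2 haematology. It does not: a site would have to overlook criterion 1 at Screening and again on Day 1, and the result would be a deviation.

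The defence on the repeat test stands in part. The acceptable range is undefined, and a site that knows criterion 1 could reasonably treat a disqualifying value as unacceptable and repeat it. Losing the repeat depends on the literal reading.

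A reader might also try to size a safety risk from the lymphocyte data in Protocol 4.2.4.1. Grade 3 lymphopenia after the first dose occurred in 1/12 at 10 µg and 1/11 at 30 µg, together 2/23 = 8.7%. To reach 0.49 (Grade 3), a subject in the Grade 2 band needs a fall of (0.50 − 0.49)/0.50 = 2.0% to (0.749 − 0.49)/0.749 = 34.6%. From Grade 1 the fall is (0.75 − 0.49)/0.75 = 34.7% to (1.00 − 0.49)/1.00 = 51.0%. The arithmetic is right, but it does not measure risk in the elderly:
- The cited US report is titled for adults aged 18 to 55, and baseline grades are not given.
- Section 4.2.4.1 calls the decrease transient and the abnormalities unrelated to clinical findings. Section 4.3.1 treats it as a short-lived effect that counts as an adverse event only with clinical consequences.
- The 2.0% is an artefact of where the band edge is rounded. With the Appendix C limit of 499 cells/mm³ it is (500 − 499)/500 = 0.2%.

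Finally, Appendix E places the haematology change in the synopsis and Section 7.2 only. That makes an oversight in 9.1.6.3 plausible, but the log is headed as listing main changes, so its silence proves little. The conflict does not depend on it.

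**Conclusion.** The inconsistency is real, lies in current text, and is confined to elderly Grade 2 haematology. It is a wrong threshold in an operational section, not an unclear design: criterion 1 states the intended limit twice and controls randomization. The exposure is a site error that leads to a deviation and possibly a per-protocol exclusion, plus a missed repeat test if the acceptable range is taken to be the limits in the preceding sentence. The number of elderly subjects with such values at screening is not given, so the frequency cannot be estimated. Sample size, power and the primary safety analysis are unaffected. It should be corrected because the limit was tightened for safety reasons and the correction is small.

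A minor separate inconsistency: adult exclusion criterion 13 covers any history of HBV or HCV infection in the trial summary, but only active infection in Section 7.1. The documents do not show which is intended.

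**What to change.** Change only the elderly clause of 9.1.6.3, leaving the adult Grade 1 limit and the 7-day window in place. For example: *…and, for the elderly, not above Grade 1 for haematology and not above Grade 2 for other laboratory values (see Section 7.2, exclusion criterion 1)*. Then state that the acceptable range for the repeat test means these limits. The cross-reference makes it less likely that the two places drift apart again.

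Separately, choose one wording for adult criterion 13 and use it in both the trial summary and Section 7.1.

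The cost is a short protocol amendment with ethics committee approval before use (Section 14.1) and, if classed as important, regulatory filing (Section 14.3). The SAP, endpoints and sample size need no change.
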